#### **10.1.2. Recurrences and Complications**

Each identified incidence of lesion recurrence, complication or adverse event recorded at any point throughout the treatment and follow-up evaluation phase will be explored descriptively. Statistical evaluation of recurrences will be as follows:

- (i) *Kaplan-Meier Survival Probability Estimates* will be calculated across the duration of available follow-up data, reporting survival probability estimates, and lower and upper limits of the 95% Confidence Interval by follow-up year.
- (ii) *Log-Rank Test* will be performed to evaluate for differences in recurrence-free survival between lesion types.
- (iii) *Multivariate Cox Regression Analysis* will be performed to account for the contribution of the potential influential factors of gender, age, lesion type, lesion size, total treatment dosage and TDF to recurrence-free survival.

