## 2 STUDY JUSTIFICATION AND RATIONALE

Non-melanoma skin cancers are the most common form of cancers with the incidence increasing at a rapid rate. Current guidelines (e.g. National Comprehensive Cancer Network (NCCN) and American Academy of Dermatology (AAD)) suggest that surgical treatments remain the most effective option for the management of most cases of BCC and SCC.

Clinical recommendations for radiation therapy (RT) are typically based on consideration of RT as a single category without differentiating between the different applications of the different available modalities. As different radiotherapy modalities and dosing have been shown to result in widely varying outcomes, with recurrence rates ranging from 2.8% to 30%, such generalized recommendations can be misleading. AAD guidelines group newer technologies such as high-dose electronic brachytherapy (EBT) and SRT as new therapies. Though the AAD has since clarified these modalities in an addendum position statement it continues to refer to SRT as a “new” technology that “differs substantially from traditional external beam radiation therapy” and one in need of “research on long term outcomes.”

This retrospective study has been designed to focus on efficacy and safety of superficial radiation therapy (SRT) for NMSC and to specifically address this AAD-highlighted deficiency and need for long-term evaluation of ‘new’ technologies for the treatment of NMSC. Evaluation of SRT for NMSC in this study will be via review of retrospective data for procedures delivered by the Sensus Healthcare SRT-100™. Sensus Healthcare’s SRT-100™ has been cleared by the U.S. Food and Drug Administration (U.S. FDA) for the treatment of non-melanoma skin cancer and keloids.

The SRT-100™ delivers a precise, calibrated dose of superficial radiation therapy that only penetrates skin deep, resulting in a virtually painless treatment can be safely administered in the physician’s office.

Low-dose SRT effectively destroys BCC and SCC without any invasive cutting, bleeding or stitching. There is no need for anesthesia, no risk of infection or scarring and no need for reconstructive plastic surgery. Healing time is quick with minimal to no post-treatment downtime or lifestyle restrictions. It is therefore both a viable and highly desirable alternative to invasive, painful and higher-risk surgical procedures.

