#### **5.2.2. Data Collection Methodology**

Patient data will be retrospectively collected from the medical records and other source documentation already existing in patient files at the participating sites.

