## **5.3. STUDY DURATION, ENROLLMENT AND NUMBER OF SITES**

### **5.3.1. Duration of Study**

Applicable data elements to be reviewed in this study will be collected from patient records whose treatment of NMSC with the SRT-100™ occurred prior to 01/01/2015. All applicable and available data elements as specified in this study protocol will be recorded for each patient from the time of treatment forward to the most recent follow-up data entry date.

Therefore, the study duration of patient participation in this study according to the duration of the review of their medical records will vary individually based upon their initial SRT-100™ treatment date.

The entire study duration with respect to time from start of patient data identification and collation to completion of the final patient data entry will be dependent upon the time needed to identify all potential participating study sites and to collate all of the required available data from all qualifying patient records at each of those sites.

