## **6. STUDY PROCEDURES**

### **6.1. RESEARCH DATA SOURCE**

The research data source in this study is existing recorded information in patient files at the study test sites from patients who received SRT-100™ treatment for NMSC prior to January 1, 2015 and for whom follow-up data is available. This study is a pure retrospective analysis. No additional information will be collected for any subject in this study other than the required information that is already existing in their patient file.

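### The recurrence analyses in 10.1.2 assume, without stating or testing it, that end of follow-up is unrelated to recurrence; the 5-year estimate could be biased in either direction

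*Combined protocol and SAP*

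**What the plan says.** Section 10.1 makes recurrence part of the primary analysis. Section 10.1.2 says Kaplan-Meier estimates "will be calculated across the duration of available follow-up data, reporting survival probability estimates". Confidence limits at the 95% level are given for each year, and a log-rank test between lesion types and a Cox model follow.

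The data behind the curve are limited in four ways:

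- **Source.** Section 5.2.2 draws on "medical records and other source documentation already existing in patient files at the participating sites". Section 6.1 adds: "No additional information will be collected for any subject in this study other than the required information that is already existing in their patient file". No tracing, contact with outside providers or record linkage is planned.
- **Window.** Under 5.3.1 each record is read "from the time of treatment forward to the most recent follow-up data entry date". No common cut-off date or minimum length of follow-up is set; 6.1 asks only for patients treated "prior to January 1, 2015 and for whom follow-up data is available".
- **Fields.** Section 6.3 F lists months to the most recent follow-up, recurrence yes or no, treatment and outcome of a recurrence, and notes. Section 6.3 lists no treatment date, time of recurrence, death or reason for end of follow-up.
- **Checks.** Section 10.2.3(ii) describes months of follow-up, tabulates them by year and compares lesion types with a t-test. Nothing relates loss to the recurrence estimate.

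**The concern.** A lesion last seen recurrence-free at 14 months is, by default, censored at 14 months and taken to have the same later hazard as lesions still being seen. With outcomes read only from the treating site's file, there are two plain ways for that to fail.

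- A patient with a recurrence may be treated elsewhere, with nothing reaching the file. Section 2 reports guidance that "surgical treatments remain the most effective option for the management of most cases of BCC and SCC", so this route is credible. The event is lost and recurrence is understated.
- A patient who is well may stop attending and return only if the lesion recurs. Recurrence-free time is lost while the events are kept, and recurrence is overstated.

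The study is justified in section 2 by the lack of long-term outcome data, and section 3 expects findings that generalise to the general patient population. The curve by follow-up year is the only planned estimate of recurrence over time. If the assumption fails, the headline is wrong by an amount the plan gives no means of gauging. The log-rank and Cox results are exposed too if loss differs between lesion types or with the covariates.

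**Working it through.** The plan states no expected recurrence rate, event count or loss rate for this study, so there is no figure of its own to reproduce.

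**Inputs**

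- Kaplan-Meier recurrence of 5.0% at 5 years: the all-tumor figure of the earlier single-practice series in section 3 (95% CI 3.2% to 6.7%; 1715 tumors).
- Share lost by year 2: not in the documents; assumed 10%, 25% or 50%, at a constant rate.
- Multiplier k on the recurrence hazard after the last visit: not in the documents; assumed 0.5, 1, 2, 3 or 5.

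**1. What a 5.0% estimate could stand for.**

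Hazard while under observation: λ = −ln(0.95)/5 = 0.01026 per year.

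Loss rate: d = −ln(1 − share lost by year 2)/2, which is 0.0527, 0.1438 and 0.3466 per year. The share lost by year 5 is 1 − exp(−5d) = 23%, 51% and 82%.

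True 5-year recurrence:

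1 − [∫₀⁵ d·exp(−dt)·exp(−λt − kλ(5 − t)) dt + exp(−5d)·exp(−5λ)]

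Example with 50% lost and k = 2: the integral is 0.7570 and the second term 0.1679, so recurrence is 1 − 0.9249 = 7.5%.

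| Lost by year 2 | k = 0.5 | k = 1 | k = 2 | k = 3 | k = 5 |
|---|---|---|---|---|---|
| 10% | 4.7% | 5.0% | 5.6% | 6.1% | 7.2% |
| 25% | 4.3% | 5.0% | 6.4% | 7.7% | 10.2% |
| 50% | 3.7% | 5.0% | 7.5% | 9.9% | 14.5% |

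For reference only, the result reaches 6.7%, the upper limit of the earlier series, at k of about 4.0, 2.2 and 1.7 respectively.

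**2. Does the direction follow from the design?**

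This step starts from a true 5-year recurrence of 5.0% and asks what Kaplan-Meier would report.

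- *Recurrences missing from the file.* If a share m of recurrences is censored instead of counted, the estimate is 1 − 0.95^(1−m). For m = 10%, 20%, 30% and 50% this gives 4.5%, 4.0%, 3.5% and 2.5%.
- *Selective return.* This was simulated with 2,000,000 lesions, potential follow-up uniform from 3 to 8 years, and visit loss of 10%, 20% or 30% a year. If a share q of recurrences after loss comes back and is recorded, q = 30% gives 5.5%, 6.3% and 7.5%; q = 50% gives 5.8%, 7.0% and 9.1%.
- *Both, with m = q = 30%.* The same three loss rates give 4.0%, 4.8% and 6.1%.
- *Neither.* The estimate returns to 5.0%.

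The sign therefore depends on m, q and the loss rate, none of which the documents give.

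**The case against.** The strongest objection concerns direction. A reader might infer that recurrences managed elsewhere simply disappear and that long-term recurrence is therefore understated. The documents do not support that.

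- Section 2 reports a guideline preference for surgery. It does not say that patients with a recurrence leave the site without a chart entry. Section 1.8 describes patients given SRT as including those who decline surgery or are poor surgical candidates, which weakens the inference.
- A recurrence treated elsewhere but noted in the site file would be captured. Section 5.2.2 covers other source documents in the file, and 6.3 F has a field for recurrence treatment and outcome with no limit on where it was given.
- Selective return pushes the estimate up and is just as open.

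All of this stands, and the point is limited accordingly.

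Two further objections also hold. Treating early loss as non-informative is the default behaviour of Kaplan-Meier, not a rule the plan writes down; the plan is silent. And lesions lost cannot be separated from lesions followed to the end of the record, because there is no cut-off, treatment date or reason for end of follow-up. A sensitivity analysis restricted to lost lesions could not be run on the fields listed.

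It can also be said that yearly confidence intervals and the follow-up distribution in 10.2.3(ii) already show where late data are thin. They do show that, but they measure precision and length of follow-up, not whether those who left differ in risk. Uncertainty about direction does not remove the need for a check: without one, a reader cannot tell which way the headline errs.

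**Conclusion.** The point holds in a two-sided form. Recurrence is read only from the treating site's file up to each lesion's own last entry. All three methods in 10.1.2 need end of follow-up to be unrelated to recurrence, and nothing in the plan states or tests this. Long-term recurrence may be biased, downward or upward.

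The size is not known. On the assumed inputs, a reported 5.0% at 5 years could stand for 4.7% to 7.2% with light loss (10% by year 2) and 3.7% to 14.5% with heavy loss (50%). These ranges rest on a constant hazard, a constant loss rate and multipliers from 0.5 to 5, none of which comes from the documents. They show sensitivity and do not predict this study's result. The 6.7% limit belongs to another series and is not a success criterion here.

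This should be changed, because it governs how firmly the long-term conclusion can be worded.

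**What to change.** In 10.1.2(i), state the censoring rule and the assumption behind it. Then add a delta-adjusted sensitivity analysis:

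- Multiply the recurrence hazard after the last visit by 0.5, 1, 2, 3 and 5 for every lesion last seen recurrence-free before 5 years, overall and by lesion type. Applying it to all such lesions avoids having to identify which were lost. It needs only the months of follow-up and recurrence status that the plan relies on for its own curve. Because it also covers lesions whose record simply ended, it widens the range on both sides.
- Report 5-year recurrence at each multiplier, with numbers at risk and numbers censored by year beside the headline, and word the long-term conclusion in the light of that range. The 6.7% limit may be shown as a reference but not used as a decision rule.

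In 6.3, add time to recurrence, death and reason for end of follow-up, extracted where the chart holds them, so that loss can be separated from administrative censoring. This must be done before the sheets linking codes to charts are destroyed under 7.2.1.

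The cost is one more analysis, a few more fields per chart, and a wider range shown beside the headline.

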## **5.4. STUDY POPULATION**

The study population comprises patients who were treated at one of the participating study sites with the SRT-100™ for one or more NMSCs, who have follow-up data and who satisfy each of the study inclusion criteria and none of the exclusion criteria.

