### **5.4.1. Inclusion Criteria**

1. Male or female.
2. Treatment with SRT-100™.
3. Treatment date of December 31, 2015 or earlier.
4. Non-Melanoma Skin Cancer (NMSC) pathological diagnosis of confirmed squamous cell carcinoma (SCC) or basal cell carcinoma (BCC).

5. Histopathological Grade: G1 (well differentiated); G2 (moderately differentiated) or Gx (not assessed).
6. One lesion is treated, or more than one lesion is treated with a minimum of a 5 mm gap between the edges of the lesion margins.
7. Required retrospective data is existing and sufficient.

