## **10. RESULTS ANALYSIS**

### **10.1. PRIMARY ANALYSIS**

Primary analysis of the retrospective data set will be assessment of cure rates and incidence of reoccurrence of lesions.

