#### **10.1.1. Cure Rate**

Cure rate will be calculated as the percentage of lesions that attained complete cure following treatment completion, reported as the overall success rate.

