#### **10.2.1. Subject Demographics**

Descriptive evaluation (mean, standard deviation and range) of the subject demographics of age and gender will be performed on a subject rather than lesion basis.

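### Patients can contribute several lesions but no analysis allows for within-patient correlation: if lesions correlate, the Kaplan-Meier interval is too narrow and Cox tests of gender and age reject too often

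*Combined protocol and SAP*

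**What the plan says.** - **Several lesions per patient.** Section 5.4 admits patients treated for "one or more NMSCs, who have follow-up data and who satisfy each of the study inclusion criteria". Section 5.4.1 accepts cases where "more than one lesion is treated with a minimum of a 5 mm gap between the edges of the lesion margins". There is no cap.
- **Outcomes counted by lesion.** The primary analysis (10.1) is "assessment of cure rates and incidence of reoccurrence of lesions". The cure rate (10.1.1) is the "percentage of lesions that attained complete cure following treatment completion".
- **Recurrence analyses (10.1.2).** Kaplan-Meier is planned, "reporting survival probability estimates, and lower and upper limits of the 95% Confidence Interval by follow-up year"; a log-rank test is to "evaluate for differences in recurrence-free survival between lesion types"; and a Cox model is "to account for the contribution of the potential influential factors of gender, age, lesion type, lesion size", total dose and TDF.
- **Secondary tests (10.2.2 to 10.2.4).** BCC and SCC are compared with t-tests for independent samples.
- **Subject-level work.** Only the age and gender summary (10.2.1) "will be performed on a subject rather than lesion basis".

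Section 10 contains no clustered or robust variance, frailty term, or resampling by patient.

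**The concern.** Kaplan-Meier with its usual variance, the log-rank test, Cox regression and the two-sample t-test all assume independent units. Lesions on one patient share that patient's skin, treating site and often follow-up, so their outcomes may be positively correlated. If they are, the lesions carry less information than their number suggests.

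- **Kaplan-Meier.** Its 95% interval is the only precision measure in the primary analysis. It would claim more certainty about long-term recurrence than the data hold.
- **Cox, gender and age.** Gender is constant and age nearly constant within a patient, so their p-values would tend to be too small. Gender is not incidental: the earlier series in section 3 reported more recurrence in tumors on men, section 3 says this study is meant to confirm and extend those findings, and section 1.5 links multiple lesions to male sex and younger age.
- **BCC versus SCC (log-rank, t-tests).** P-values can be too small if a patient's lesions tend to share a type, too large if types tend to differ within a patient, and near nominal if type is unrelated within a patient.

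**Working it through.** The plan states no sample size, event count or expected interval width, so there is no figure of its own to reproduce. What follows is illustration.

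**Inputs**
- Lesions per patient: 5.4/3.3 = 1.636, from the US annual figures in section 1.4. This is a background ratio for all treatments, not a study estimate. A lower value of 1.2 is also tried.
- Spread of lesion counts: geometric (assumed).
- ICC: 0.05 to 0.3 (assumed).
- Test level: two-sided 5%. The plan states this for the t-tests only; it is assumed for Cox and log-rank.
- Scale: the earlier series' 5-year recurrence of 5.0% (3.2% to 6.7%), section 3, treated as if it were an unclustered interval.

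**Formula**

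Design effect DE = 1 + (E[m²]/E[m] − 1) × ICC. For a geometric count, E[m²]/E[m] − 1 = 2 × mean − 2, which is 1.273 at mean 1.636 and 0.4 at mean 1.2. The interval should be √DE times as wide. A patient-level test at nominal 5% has true error 2 × (1 − Φ(1.96/√DE)).

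| Mean lesions | ICC | DE | √DE | True error |
|---|---|---|---|---|
| 1.64 | 0.05 | 1.064 | 1.031 | 5.7% |
| 1.64 | 0.10 | 1.127 | 1.062 | 6.5% |
| 1.64 | 0.30 | 1.382 | 1.176 | 9.5% |
| 1.2 | 0.05 | 1.020 | 1.010 | 5.2% |
| 1.2 | 0.30 | 1.120 | 1.058 | 6.4% |

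On the earlier series' scale:
- ICC 0.05: 5.0 − 1.8 × 1.031 = 3.1 and 5.0 + 1.7 × 1.031 = 6.8.
- ICC 0.3: 5.0 − 1.8 × 1.176 = 2.9 and 5.0 + 1.7 × 1.176 = 7.0.

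How strong these ICCs are: at 5% risk, once one lesion recurs a second lesion's risk is 0.05 + ICC × 0.95, which is 9.8% at ICC 0.05 and 33.5% at ICC 0.3.

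**Simulation of the planned Cox model**

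All six factors had no effect. Recurrence was 5% at 5 years, follow-up of 1 to 8 years was shared within a patient, and shared gamma frailty had variance 1 or 8 (ICC 0.048 or 0.288). Wald tests at 5%, 20,000 replicates. Each cell gives ICC 0.048 / 0.288.

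| Events | Gender, unclustered | Gender, clustered | Age, unclustered | Age, clustered |
|---|---|---|---|---|
| about 22 | 4.9% / 7.9% | 4.6% / 5.3% | 5.9% / 9.0% | 7.4% / 7.8% |
| about 48 | 5.4% / 8.6% | 4.9% / 5.0% | 5.8% / 9.4% | 6.1% / 6.5% |
| about 95 | 5.5% / 8.8% | 4.8% / 4.9% | 5.8% / 9.0% | 5.6% / 5.5% |

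The clustered score test (6,000 replicates) ran at 4.3% to 5.2% for gender and age at 22 events and 4.6% to 5.0% at 48. Five-year Kaplan-Meier coverage at 48 events was 94.5% / 91.1% unclustered and 95.0% / 94.4% clustered. The clustered standard error averaged 1.02 and 1.12 to 1.14 times the usual one.

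**More lesions per patient**

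A separate simulation (about 1,715 lesions, about 73 events, 2,000 replicates) gave, at three lesions per patient and unclustered, gender error of 6.5% at frailty variance 1 and 10.1% to 14.6% at variance 4. At variance 8 with uneven counts it was 17.1%, with 5-year coverage of 80.8%. Patient-clustered tests ran at 4.0% to 5.4% across all its scenarios.

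**BCC versus SCC**

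Unclustered error in 20,000 replicates of 1,000 patients, ICC about 0.3:

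| Types within patient | t-test | Log-rank |
|---|---|---|
| Match | 9.2% | 9.4% |
| Unrelated | 5.1% | 5.0% |
| Alternate | 3.2% | 3.2% |

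At ICC 0.05 all ran between 4.7% and 5.7%. Clustered versions ran at 4.9% to 5.2%.

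The simulations restate the assumed correlation; they are not evidence for it.

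**The case against.** - **The size rests on assumed inputs.** This stands. With equal lesion counts at 1.64 per patient, DE = 1 + 0.636 × ICC and the multiplier is only 1.016 to 1.091. The 18% end needs uneven counts and ICC 0.3 together.
- **At weak correlation the harm is negligible.** This also stands. At ICC about 0.05, simulated coverage is 94.5% and unclustered gender tests run at 4.9% to 5.5%.
- **Not all the excess is clustering.** With no correlation, a separate run gave 4.4% for gender and 5.5% for age at 22 events, and 4.2% and 5.0% at 47. Most of the excess in the 5.9% for age at 22 events and ICC 0.05 is therefore a small-sample effect.
- **The t-tests are secondary and can err either way.** True, and ICC 0.3 has no particular basis for dose, kV or follow-up months. But independence is written into those tests while one patient may hold both types, and the remedy is simple.
- **Clustered Wald tests can be worse.** For age at 22 events and ICC 0.05 they ran at 7.4% against 5.9% unclustered. This is the reason to prefer the score test.
- **The unit is inferred.** Section 10.1.2 never says per lesion. The reading follows from 10.1, 10.1.1, 10.2.1 and the lesion-level covariates; the silence itself needs correcting.
- **Site clustering is not addressed.** Correct, and a separate question.

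None of this removes the defect. It limits how large the effect can be said to be.

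**Conclusion.** The concern holds, conditionally on positive within-patient correlation. In that case the direction is firm for the Kaplan-Meier interval and for the Cox tests of gender and age; for BCC versus SCC it depends on how types fall within patients.

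The size cannot be fixed from the documents. It is slight with few lesions per patient and weak correlation, and material with many or uneven counts and strong correlation. Since point estimates are unaffected and no success threshold depends on the interval, this should be fixed but does not undermine the study.

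**What to change.** **Section 10.1.2**
- State the lesion as the unit and the patient as the cluster.
- Report patient-clustered 95% intervals for Kaplan-Meier, by robust variance or by bootstrap of patients.
- Fit Cox with a sandwich variance clustered on patient, and take factor p-values from the patient-clustered score test.
- Say how hazard-ratio intervals are formed, since clustered Wald intervals share the weakness seen with few recurrences.
- Replace the plain log-rank test with the robust score test from a Cox model of lesion type.

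**Sections 10.2.2 to 10.2.4**
- Replace the independent-samples t-tests with linear models using patient-clustered standard errors.

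**Data file and reporting**
- Keep the per-patient code of sections 7 and 7.2.1 in the analysis file, enter all of a patient's lesions under that one code, and add a lesion number, which section 6.3 lacks. Do this before the link sheets are destroyed (7.2.1); afterwards the grouping may not be recoverable.
- Report patients, lesions and recurrences beside each estimate.

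**Cost.** SAP wording, one database column and a few lines of code. Intervals will usually be slightly wider. With about 22 recurrences clustered intervals are still imperfect: one simulation at frailty variance 8 gave 5-year coverage of 92.1% clustered against 89.7% unclustered.

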### 3. SUPPORTIVE LITERATURE

The following study published in 2012 is similar in design and purpose to the current retrospective trial.

Superficial x-ray in the treatment of basal and squamous cell carcinomas: A viable option in select patients

J Am Acad Dermatol December 2012 Volume 67, Issue 6, Pages 1235–1241

[name], Brett M. Howard, BA, Henry P. Heaton, BA, [name], Hyokyong [name], and W. [name]

The abstract from this publication is presented below.

*Background:* Effective nonsurgical modalities are limited in the treatment of basal cell carcinoma (BCC) and squamous cell carcinoma (SCC).

*Objective:* We sought to evaluate the efficacy and viability of superficial x-ray therapy in the treatment of BCC and SCC in an outpatient setting.

*Methods:* A retrospective analysis was performed on 1715 histologically confirmed primary cutaneous BCC and SCC treated with superficial x-ray therapy at Dermatology Associates of Tallahassee in Florida between 2000 and 2010.

*Results:* Of the 1715 tumors reviewed during this period, 712 were histologically proven BCC (631 nodular and 81 superficial), 994 were SCC (861 SCC in situ and 133 invasive SCC), and 9 displayed distinct features of both BCC and SCC in the same biopsy specimen. Kaplan-Meier estimates (with 95% confidence intervals) of cumulative recurrence rates of all tumors at 2 and 5 years were 1.9% (1%-2.7%) and 5.0% (3.2%-6.7%), respectively; of BCC at 2 and 5 years were 2% (0.8%-3.3%) and 4.2% (1.9%-6.4%),

respectively; and of all SCC at 2 and 5 years were 1.8% (0.8%-2.8%) and 5.8% (2.9%-8.7%), respectively. Tumors on male patients and those with a diameter greater than 2 cm were associated with a statistically significant increase in recurrence likelihood.

*Limitations:* This study represents only patients treated in 1 dermatology office in North Florida and may not be representative of the general patient population.

*Conclusions:* Superficial x-ray therapy remains a viable nonsurgical option for the treatment of primary BCC and SCC in patients where surgical intervention is declined, inadvisable, or potentially associated with significant cosmetic or functional limitations.

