#### **A. Patient Information and Demographics:**

1. Gender
2. Age at treatment start

3. Ethnicity
4. Significant comorbidities

B. Lesion Diagnostic Variables and Characteristics:

1. Pathology diagnosis
2. Diagnosis subtype/variant
3. Other pathology
4. Recurrent lesion (yes/no)
5. Previous treatment if recurrent
6. Lesion location (no restrictions): scalp, mastoid, forehead, cheek, nose, ear, chin, lips, neck, upper arm, lower arm, hand, upper leg, lower leg, foot.

C. Lesion Size and Margins:

1. Lesion size
2. Treatment margin
3. Lead cutout size
4. Applicator size

D. Treatment Dosage and Schedule:

1. Treatment dose
2. Number of treatments
3. Number of treatments per week
4. Treatment span(days)

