#### **10.2.2. Lesion Variables**

- (i) *Lesion Type and Location*: The distribution (number and percentage) of lesion type (BCC and SCC) and the distribution of lesion subtype within each lesion type will be

calculated. The distribution of the location of lesions on the body will also be calculated. The findings will be presented descriptively in table and chart format.

- (ii) *Comorbidities*: The distribution (number and percentage) of comorbidities for lesions overall and by lesion type will be calculated and presented descriptively in table and chart format.
- (iii) *Lesion Size*: Descriptive evaluation (mean, standard deviation and range) of baseline lesion size (diameter) in centimeters (cm) will be calculated for lesions overall and by lesion type. T-test analysis for two independent samples will be applied to assess for any difference in lesion size between lesion types. A two-tailed p value of <0.05 will be considered statistically significant and indicative of a clinically meaningful difference. The categorical distribution (number and percentage) of lesion size for all lesions and by lesion type will also be calculated.

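### The log-rank test and Cox model use lesion type as BCC versus SCC, so SCC in situ and invasive SCC are averaged although subtype is collected

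*Combined protocol and SAP*

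**What the plan says.** Section 10.1.2(ii) specifies a log-rank test that "will be performed to evaluate for differences in recurrence-free survival between lesion types", without listing the levels. The Cox model in 10.1.2(iii) covers "gender, age, lesion type, lesion size, total treatment dosage and TDF to recurrence-free survival"; it has a lesion-type term and no term for subtype or invasiveness. The Kaplan-Meier estimates in 10.1.2(i) are not broken down by any class.

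The levels are given in 10.2.2(i): "The distribution (number and percentage) of lesion type (BCC and SCC) and the distribution of lesion subtype within each lesion type will be" calculated and shown in tables and charts. Type and subtype are thus two variables, one nested in the other. Section 10.2.2(iii) fits a two-level reading: "T-test analysis for two independent samples will be applied to assess for any difference in lesion size between lesion types".

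Section 1.7 lists in situ/Bowen's disease and invasive SCC as two of eleven SCC variants, and the inclusion criteria in 5.4.1 admit any confirmed SCC of grade G1, G2 or Gx. Section 6.3 B collects "Diagnosis subtype/variant". Apart from the distribution in 10.2.2(i), no planned analysis uses it. The cure rate in 10.1.1 is a single percentage of lesions, "reported as the overall success rate".

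**The concern.** A secondary objective (5.1.2) is to look for differences in outcome by lesion variables, including tumour type. A pooled SCC curve estimates an average over in situ and invasive disease, weighted by whatever mix the charts contain. If recurrence differs between the two classes, the average describes the smaller class poorly, and a reader who sees only the pooled curve cannot tell.

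The only mix in the documents is in Section 3, for the study this registry sets out to confirm and extend: "994 were SCC (861 SCC in situ and 133 invasive SCC"). With a similar mix here, the SCC estimate would rest mostly on in situ lesions but could be read as applying to invasive SCC. The BCC versus SCC comparison could also look null while invasive lesions did worse.

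**Working it through.** **Inputs, all from the abstract in Section 3.** SCC: 861 in situ, 133 invasive, 994 in total. Five-year cumulative recurrence: all SCC 5.8% (95% CI 2.9% to 8.7%); BCC 4.2% (1.9% to 6.4%). The abstract gives no recurrence rate by SCC class, and the plan gives no sample size or expected number of events.

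**Reproducing the stated counts.** 861 + 133 = 994. The in situ share is 861/994 = 86.6% and the invasive share is w = 133/994 = 13.4%.

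**What a pooled 5.8% is compatible with.** Let r be the invasive-to-in-situ ratio of 5-year risks, which is an assumption. Then in situ risk = 5.8% / ((1 − w) + w·r), and invasive risk is r times that.

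- r = 1: 5.8% in both classes; nothing is hidden.
- r = 2: 5.8 / (0.866 + 0.268) = 5.1% in situ, 10.2% invasive.
- r = 3: 5.8 / (0.866 + 0.401) = 4.6% in situ, 13.7% invasive.

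In situ lesions would supply 0.866 × 5.12 / 5.8 = 76% of SCC recurrences at r = 2 and 68% at r = 3.

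**Sensitivity to the mix.** At r = 3 and the same pooled 5.8%, an invasive share of 25%, 40% or 50% gives an invasive risk of 11.6%, 9.7% or 8.7%. The gap from the pooled figure narrows as the invasive share grows, but it stays between 2.9 and 5.8 points.

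**What the BCC versus SCC contrast shows on the cited figures.** The standard errors implied by the intervals are (8.7 − 2.9)/(2 × 1.96) = 1.48 points for SCC and (6.4 − 1.9)/(2 × 1.96) = 1.15 points for BCC. The difference is 5.8 − 4.2 = 1.6 points, with standard error √(1.48² + 1.15²) = 1.87. The 95% interval is about −2.1 to 5.3 and p is about 0.39. That result fits every value of r above.

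**How precise an invasive estimate would be.** Take 133 invasive lesions and an assumed 10% recurrence. If all were followed for five years, the simple binomial interval would be 10% ± 1.96 × √(0.1 × 0.9/133) = 4.9% to 15.1%. The cited study shows this is too optimistic. An uncensored binomial standard error for all SCC would be √(0.058 × 0.942/994) = 0.74 points, against the 1.48 implied by the published interval. The information retained is (0.74/1.48)² ≈ 25%, so 133 lesions act like about 33. The simple interval becomes roughly 0% to 20%, and the Wilson interval 4% to 25%.

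**Power for in situ versus invasive at the cited numbers** (two proportions, two-sided 5%). Ignoring censoring, it is about 62% at r = 2 and 94% at r = 3. With both groups scaled to 25% (about 216 and 33 lesions), it is about 27% and 54%.

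**The case against.** Several objections have force.

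- **The mix here is unknown.** A reader might infer that this registry's SCC result will be mainly an in situ result. The documents do not support that. The 861:133 split comes from one dermatology office, whose abstract warns that it may not be representative, and Section 3 says this study will draw on numerous sources. What stands is conditional: pooling averages two classes, and with a mix like the cited one the average leans to in situ.
- **No excess invasive risk is shown.** A reader might also infer that invasive SCC is known to recur more often after this treatment. The cited abstract reports SCC recurrence only pooled, so ratios of 2 and 3 are illustrations.
- **The pooled figure is not purely an in situ figure.** Even with the cited mix, invasive lesions supply about 32% of SCC recurrences at r = 3.
- **A split estimate may be weak.** With censoring like the cited study's, the invasive interval is wide and power is modest. This argues against modelling all eleven variants. It does not argue against showing one basic split with its interval.
- **The plan partly covers this.** Section 10.1.2 will describe each recurrence, and 10.2.2(i) will tabulate subtype counts, so the raw counts would exist. The plan nevertheless commits to no cure or recurrence result by SCC class.
- **The t-tests are not affected.** They compare lesion size, treatment days, follow-up time, dosage variables and visit frequency. None compares outcomes.

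**Conclusion.** The point holds in conditional form. Section 10.1.2 read with 10.2.2(i) makes lesion type a two-level factor in the log-rank test and the Cox model, so SCC in situ and invasive SCC are averaged while the field that could separate them feeds only a frequency table. If the registry's mix resembled the cited one, a pooled 5.8% at five years could conceal nothing (r = 1) or an invasive rate of 10.2% (r = 2) or 13.7% (r = 3). These figures rest on three assumptions: the cited mix, the cited pooled rate, and the risk ratio. The documents establish neither that in situ lesions will dominate this registry nor that invasive lesions recur more often. The split is justified because the pooled analysis cannot answer either question and the data to do so are already being collected.

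**What to change.** Before analysis:

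1. State a rule that assigns each SCC variant listed in Section 1.7 to in situ, invasive or unspecified. The subtype field is not itself an in situ/invasive flag, and some charts may give no subtype, so the unspecified category is needed.
2. In 10.1.1 and 10.1.2(i), report cure rate and Kaplan-Meier estimates with 95% intervals for BCC, SCC in situ and invasive SCC. Show unspecified SCC separately and keep total SCC.
3. In 10.1.2(ii), run the log-rank test across BCC, SCC in situ and invasive SCC. In 10.1.2(iii), use the same levels for lesion type.
4. Leave the t-tests as they are.

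The cost is at least one extra degree of freedom, a small mapping task and a few extra curves; no new data fields are needed. The invasive estimate will be imprecise. With 133 invasive lesions at 10% and censoring like the cited study's, the 95% interval is roughly 4% to 25% rather than 4.9% to 15.1%, so it should always be shown with its interval.
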